7.2 Derived variables

Variable	Definition	Unit
Duration (assessment to surgery) (DA_S)	Difference between assessment date and surgery date	Number of days
Duration (biopsy to assessment) (DB_S)	Difference between biopsy date and surgery date	Number of days
Implementation of same day biopsy	Percent of cases with DB_S=0 (start of site participation to study end)	Percent
Operative time	Difference between stop and stop times	Minutes

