3.2 Endpoints

Primary Endpoint: The number of patient visits to the breast center for invasive procedures from the time of biopsy to surgery.

Secondary Endpoint:

1. Device success: percent successful localization, detection and retrieval;
2. Device safety: rate of device-related adverse events;
3. Procedural success: absence of close margins (DCIS: <2mm), positive margins (tumor on ink) or requirement for re-excision.
4. Duration (days) from assessment to surgery and biopsy to surgery;
5. Radiologist assessment: ease of placement; ability to position reflector in desired location; scheduling flexibility; visibility on ultrasound/ mammography (immediate and late); artifact (Tomo/MRI if applicable).
6. Surgeon assessment: ease of detection; ease of device retrieval.
7. Participant satisfaction questionnaire: anxiety; convenience; pain; overall experience compared to expectation
8. Process improvement with implementation of same-day biopsy and SAVI SCOUT® placement.

[figure not shown]
4 Study Methods

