4.1 General Study Design and Plan

This is a single-arm, multicenter, non-randomized cohort study. This is a non-blinded study with no active control for this study. However, the primary endpoint will be compared to historical controls.

The registry is divided into three periods:

1. Inclusion Period: from registry eligibility screening until reflector insertion;
2. Device Period: from reflector insertion at biopsy to removal at surgery;
3. Outcomes Period: from completion of surgery to pathology report of outcomes.

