6.2.2 Intention-to-treat (ITT) Population

The ITT population includes all participants in whom the SCOUT® Reflector has been inserted. Any participants who have a reflector inserted and do not undergo surgery will be exited from the registry using a study completion form. The occurrence of this scenario is expected to be low ($\leq 10\%$). Reasons may include:

1. Benign concordant biopsy results.
2. Participant death prior to surgery due to metastases.
3. Lesion is metastatic from another location.
4. Participant declines surgery.

5. Participant is ineligible for surgery.

Descriptive data and adverse event analysis will be performed on the ITT analysis set. The PP and ITT endpoints will be calculated separately and compared. Differences between their results will be summarized and discussed.

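### The SAP 7.2 rule for same-day biopsy (DB_S = 0) counts surgery on the biopsy date, so it does not measure same-day biopsy

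*SAP*

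**What the plan says.** Three rows of the derived-variable table in SAP 7.2 matter here.

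- The first, "Duration (assessment to surgery) (DA_S"), runs from the assessment date to the surgery date, in days.
- The second is labelled "Duration (biopsy to assessment) (DB_S"), but its definition column reads "Difference between biopsy date and surgery date".
- The third, implementation of same-day biopsy, is "Percent of cases with DB_S=0 (start of site participation to study end").

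SAP 3.2 lists secondary endpoint 4 as "Duration (days) from assessment to surgery and biopsy to surgery" and secondary endpoint 8 as "Process improvement with implementation of same-day biopsy and SAVI SCOUT® placement". SAP 6.2 makes reflector insertion at biopsy a condition of enrolment. The schedules of assessments in Protocol 4.9 and SAP 4.4 hold one shared date for biopsy and insertion, a separate assessment date, and a surgery date. SAP section 13 records no changes, and no other section corrects the rows in 7.2.

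**The concern.** The label and the definition of DB_S name different intervals, and the same-day rule is built on DB_S. Under the definition, DB_S = 0 means that surgery took place on the biopsy date. That is not what the row claims to report.

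A participant biopsied on the day of assessment and one biopsied two weeks later would both be classed as not same-day whenever surgery falls after the biopsy date. A programmer following the table would then report a figure near zero that reflects the formula rather than practice at the sites. The registry's title announces an analysis of process improvement, and this is the only derivation whose wording matches the process-improvement endpoint. A misleading figure could therefore be read as a finding about workflow.

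**Working it through.** The plan gives no figure to reproduce. The check sets the rows side by side and applies them to assumed dates.

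**Step 1: what DB_S means.** Four items point to biopsy to surgery:
- the definition column of the row itself;
- the suffix _S, which stands for surgery in the companion name DA_S;
- the parallel DA_S row, which also ends at surgery;
- endpoint 4, which needs a biopsy-to-surgery duration in the Protocol synopsis, Protocol 4.2 and SAP 3.2.

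Only the label points to assessment. The working definition is therefore DB_S = surgery date − biopsy date.

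**Step 2: apply the rule.** Let DA_B = biopsy date − assessment date. The dates below are assumptions for illustration.

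| Case | Assessment | Biopsy | Surgery | DB_S | DA_B | Counted by DB_S = 0 | Biopsy on assessment day |
|---|---|---|---|---|---|---|---|
| (i) | day 0 | day 0 | day 30 | 30 − 0 = 30 | 0 − 0 = 0 | no | yes |
| (ii) | day 0 | day 14 | day 30 | 30 − 14 = 16 | 14 − 0 = 14 | no | no |

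The rule treats both cases alike. This does not depend on day 30: for any surgery date after the biopsy date, DB_S is above 0 and the case is not counted, whatever the assessment date.

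**Step 3: expected size.** The documents give no distribution of dates, so the percentage cannot be calculated. Two passages suggest that surgery on the biopsy date is not the expected pathway. SAP 4.1 sets out a "Device Period: from reflector insertion at biopsy to removal at surgery". SAP 6.2.2 gives "Benign concordant biopsy results" as a reason for leaving without surgery, which implies that the biopsy result is normally known before an operation. Hence the expectation of about 0%.

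**Step 4: which interval could be meant.** There are three candidates.
- Biopsy and surgery: the rule as written, expected to be about 0%.
- Biopsy and reflector placement: 100% of enrolled participants, because enrolment requires insertion at biopsy and the two share one date field.
- Assessment and biopsy: the candidate not fixed near either extreme by the design.

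Protocol 2.3 gives some support to the third, since it says that placing the reflector at the diagnostic work-up could save two visits. It does not mention assessment or same-day biopsy by name.

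**Step 5: is information lost?** For an operated participant, DA_S − DB_S = (surgery − assessment) − (surgery − biopsy) = biopsy − assessment = DA_B. In case (ii), 30 − 16 = 14. The dates needed are in the database; what is missing is a correct derivation.

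**The case against.** The strongest defence is that this is clerical. The registry is descriptive and not hypothesis driven, all dates are collected, and the same table has another evident slip: operative time is defined from stop to stop. That stands as a limit on severity. It does not remove the point, because the obvious repair, correcting the DB_S label, leaves the same-day rule on the wrong interval.

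A reader might infer more, namely that the label conflict puts endpoint 4 at risk as well, so that either endpoint 4 or the same-day rule must fail. The documents do not support this. The evidence in step 1 settles the meaning of DB_S as biopsy to surgery, and endpoint 4 then has the variable it needs. Even under the label reading, it would lose a named derivation and not its data.

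Two further cautions stand. First, the SAP does not state that this row serves endpoint 8. That endpoint speaks of same-day biopsy and placement, the row of same-day biopsy only, so the link is inferred from the wording. Second, neither document defines 'assessment'. Where the synopsis and SAP 3.2 start the first interval of endpoint 4 at assessment, Protocol 4.2 starts it at diagnosis. A new variable that begins at assessment has no settled meaning until this is resolved.

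**Conclusion.** Wrong as written, with an effect limited to one descriptive secondary item. The same-day percentage in SAP 7.2 counts surgery on the biopsy date and cannot identify same-day biopsy.

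That conclusion rests on reading DB_S by its definition. The figure of about 0% is an inference from the pathway described. That endpoint 8 is the item affected is likely, not established. That same-day assessment and biopsy was intended is plausible, but it is for the sponsor to confirm.

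**What to change.** In SAP 7.2:

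1. Relabel DB_S as the duration from biopsy to surgery and keep its definition for endpoint 4.
2. Add a duration from assessment to biopsy (DA_B), equal to biopsy date minus assessment date, in days, taken directly from the two recorded dates. State which date counts as assessment, and reconcile it with the diagnosis-to-surgery wording in Protocol 4.2.
3. Ask the sponsor to confirm that same-day assessment and biopsy is the intended meaning. If so, derive the implementation of same-day biopsy as the percentage with DA_B = 0 among enrolled participants with both dates. Keep the existing time frame, from the start of site participation to study end. State whether the row is the derivation for endpoint 8.

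The cost is low: two edited rows, one added row, one definition and one sponsor confirmation. No new data item is needed, because both dates are already in the schedules of assessments.

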7.3 Protocol Deviations

MINOR DEVIATION: a violation that does not impact the patient's rights, safety or welfare, compromise the integrity of study data and/or affect subject's willingness to participate in the study.

Examples:

- Missing original signed and dated consent form (only a copy is available)
- Missing pages of consent form
- Failure to follow study procedure (that does not affect patient safety)
- Failure to perform a laboratory test

MAJOR DEVIATION: a violation that may impact the patient's rights, safety or welfare, affect the integrity of study data and/or affect subject's willingness to

participate in the study.

Examples:

- Failure to obtain informed consent
- Enrollment of a patient not meeting all eligibility criteria
- Failure to report a serious adverse event

Deviations that impact the primary endpoint calculation will be identified and associated participant data will be assessed separately as well as with the cohort to identify the impact to the final calculation. An example of this would be if the participant was intentionally booked for a “back-up wire” prior to surgery due to lack of physician confidence or poor planning.

7.4 Demographic and Baseline Variables

Variable	Type of data/ unit
Age	Continuous/ Yrs
Height	Continuous/ Meters
Weight	Continuous/ Kg
Diagnosis	Categorical
BiRads classification	Categorical

7.5 Procedure Variables

Variable	Type of data/ unit
Lesion type	Categorical
Guidance type	Categorical
Lesion location	Categorical
Morphology classification	Categorical
Lesion size	Continuous/ mm
Lesion depth	Continuous/ cm
Reflector detection	Nominal
Deployment within lesion	Categorical
Distance from lesion	Continuous/ mm
Type of surgery	Categorical
Retrieval success	Nominal

7.6 Treatment Variables

Variable	Type of data/ unit
Neoadjuvant therapy	Nominal
Duration of neoadjuvant therapy	Calculation (start- stop date)/ days
Number of visits for invasive procedures	Continuous

8 Utility Analyses

Number of visits for invasive procedures will be reported as: number, mean, standard deviation (SD), minimum, median and maximum values.

The primary endpoint will be compared to historical data using one-way analysis of variance.

9 Performance Analyses

Device and procedure success will be calculated as a percentage of the total number of cases, as well as the total number of reflectors used in the study.

10 Safety Analyses

- All reported adverse events will be categorized and described.
- Frequency and/ or percentage will be reported
- Adverse device effects (ADE) rates will be calculated separated
- ADEs will be sub-classified as appropriate
- Each participant will only be counted once and any repetitions will be ignored; the denominator will be the total population size
- Serious Adverse Events: A table of all anticipated and unanticipated serious adverse events, grouped by organ system, with number and frequency of such events in each arm/group of the clinical study. (See Adverse Events definition below).
- Other (Not Including Serious) Adverse Events: A table of anticipated and unanticipated events (not included in the serious adverse event table) that exceed a frequency threshold (for example, 5 %) within any arm of the clinical study, grouped by organ system, with number and frequency of such events in each arm/group of the clinical study.

11 Satisfaction Analyses

Clinician and participant satisfaction assessment data will be categorized and reported as frequency data.

12 Reporting Conventions

P-values ≥ 0.001 will be reported to 3 decimal places; p-values less than 0.001 will be reported as " <0.001 ". The mean, standard deviation, and any other statistics other than quantiles, will be reported to one decimal place greater than the original data. Quantiles, such as median, or minimum and maximum will use the same number of decimal places as the original data.

13 Summary of Changes to the Protocol and/or SAP

n/a

14 References

CADTH, 2019: CADTH rapid response report: summary with critical appraisal. Magnetic seed localization for soft tissue lesions in breast patients: Clinical effectiveness, cost- effectiveness, and guidelines.

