### **4.2 Endpoints**

The primary endpoint is the number of patient visits to the breast center for invasive procedures from the time of biopsy to surgery. The primary endpoint will be compared to historical controls. It is expected that there will be a mean reduction of at least one (1) visit for invasive procedures.

The secondary endpoints are defined below:

1. Device success: percent successful localization, detection and retrieval.
2. Device safety: rate of device-related adverse events.
3. Procedural success: absence of close margins (<2mm), positive margins (tumor on ink) or requirement for re-excision.
4. Duration (days) from diagnosis to surgery and biopsy to surgery.
5. Radiologist assessment: ease of placement; ability to position reflector in desired location; scheduling flexibility; visibility on ultrasound/ mammography (immediate and late); artifact (Tomo/MRI if applicable).
6. Surgeon assessment: ease of detection; ease of device retrieval.
7. Participant satisfaction questionnaire: anxiety; convenience; pain; overall experience compared to expectation
8. Process improvement with implementation of same-day biopsy and SCOUT® Reflector placement.

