#### 4.7 Device Period

Insertion of the SCOUT® Reflector shall be conducted according to the IFU at the time of biopsy. The physician will follow regular clinical practice before and during the biopsy procedure.

SCOUT® Reflector may be inserted in a soft tissue biopsy site or a soft tissue site intended for surgical removal as per IFU and clinician decision. Additionally, as per clinician decision, more than one (1) SCOUT® Reflector may be inserted in a participant (bracketing) ensuring a minimum distance of 25 mm between Reflectors.

The data collected during the biopsy and reflector insertion will consist of the following:

- Patient demographic: age, weight, height and diagnosis
- Date of assessment
- Date of biopsy and insertion
- Reflector insertion data: success, deployment within lesion or distance from lesion, depth of reflector, type of guidance used, number of reflectors used, type of lesion
- Lot number(s) and model of the SCOUT® Reflector

- Reflector detection (if performed)
- Adverse events (if applicable)

The data collected during the surgery will consist of the following:

- Date of surgery
- Neoadjuvant therapy (if applicable): start and stop date
- Reflector detection: success before or after incision
- Reflector retrieval data: success, identification and retrieval duration
- Operative time: Time from beginning the detection to the time the lesion is removed from the breast.
- Participant satisfaction questionnaire: this may be completed by/collected from the participant up to 2 weeks after the surgery.
- Adverse events (if applicable)

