#### **4.8 Final Outcomes**

The assessment of procedure success is determined by the pathology report. This will not require an additional participant visit for the purposes of the registry. Participation will be considered complete following collection of the final outcomes and Participant satisfaction questionnaire.

The following data points will be recorded from the report:

- Excised tissue information
- Specimen size
- Margins: (positive, close, negative)
- Re-excision required (after surgery)
- Radiologist assessment (collected once per radiologist at completion of study)
- Surgeon assessment (collected once per surgeon at completion of study)

---

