6.2.1 Per Protocol Population

The per protocol (PP) population will include all consented participants in whom a SCOUT® Reflector has been inserted and who subsequently undergo breast surgery.

Endpoint analysis will be performed on the PP analysis set.

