7.1 Variable Assessment

Variable	CRF and data point
Inclusion	Inclusion CRF_Reflector Location
Per protocol completion	Surgery CRF_Type of surgery
Intention to treat completion	Study Completion CRF_Reason for completion
Device insertion success	Inclusion CRF_Deployment within lesion
Device retrieval success	Surgery CRF_Reflector retrieval success
Procedural success	Outcomes CRF_Margin assessment
Efficiency endpoint	Additional visit CRF_Number of visits
Device Safety	Adverse Event CRF_Device Related

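### Procedural success is divided by all cases, with no rule for operated participants whose specimen contains no tumour, so the margin failure rate can be understated

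*SAP*

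**What the plan says.** SAP section 3.2 defines the endpoint as "Procedural success: absence of close margins (DCIS: <2mm), positive margins (tumor on ink) or requirement for re-excision". Protocol section 4.2 has the same three components but does not tie the close-margin limit to DCIS; that difference does not affect this point. Neither definition requires tumour to be present in the specimen.

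For the denominator, SAP section 9 states "Device and procedure success will be calculated as a percentage of the total number of cases", and also as a percentage of all reflectors used. SAP section 6.2.1 adds "Endpoint analysis will be performed on the PP analysis set". That set needs a reflector and later breast surgery; histology plays no part.

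Protocol section 4.8 lists the margin data as "Margins: (positive, close, negative". The assessment schedules in both documents put the line between close and negative at 2 mm. SAP section 7.1 takes procedural success from "Outcomes CRF_Margin assessment". Re-excision is collected but is not mapped to the endpoint in that table.

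Neoadjuvant treatment is expected in some participants: Protocol section 4.7 records "Neoadjuvant therapy (if applicable): start and stop date". SAP section 6.3 analyses them separately, but they also stay in the full cohort.

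**The concern.** A margin is a distance from tumour to the cut edge. A specimen without tumour has no such distance, so it cannot show a close or positive margin. Under a definition built on absence it passes by default, and under an all-case denominator it is counted.

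Such specimens are foreseeable. The reflector is placed at biopsy, before histology is known. Protocol section 2.1 puts the malignancy risk at above 50% up to 95% for BI-RADS 4C and above 95% for BI-RADS 5. Benign concordant biopsy is given as a reason for not having surgery, but other benign lesions may still be excised and enter the per-protocol set. Some participants given neoadjuvant therapy may have no residual tumour.

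Procedural success is one of the measures by which SAP section 2.2 judges performance. Cases that cannot fail on margins make it look better, by an amount that depends on case mix. SAP section 6.5.2 also compares endpoint data between sites, and that comparison would pick up differences in BI-RADS 4C share, neoadjuvant use and coding habit.

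**Working it through.** The plan states no procedural success rate, target or assumed margin failure rate, so there is no figure to reproduce. The check is dilution arithmetic.

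**Inputs**
- Per-protocol size: 500 × (1 − 0.10) = 450, using the planned enrolment and the expected ceiling of 10% without surgery.
- p, the failure rate among margin-evaluable cases: 23%, an assumption. It borrows the Canadian re-excision figure in Protocol section 2.1 for scale only.
- f, the share of operated cases with no tumour in the specimen: not in the documents; 5% to 20% assumed.

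**Are benign lesions plausible in the operated set?** Suppose half of participants are BI-RADS 4C (assumed). At the risk floors, the benign share at enrolment is 0.5 × 0.50 + 0.5 × 0.05 = 27.5%. With 4C at 95% risk and BI-RADS 5 at 100%, it is 0.5 × 0.05 = 2.5%. At most 10% are expected to miss surgery for any reason. Towards the upper end, benign excisions must occur; at the lower end they might all leave before surgery. Specimens without residual tumour after neoadjuvant therapy come on top.

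**Effect of coding.** Take tumour-free cases without re-excision:
- coded negative: failure rate = p(1 − f)
- left blank and dropped: failure rate = p
- left blank and scored as non-success: failure rate = p(1 − f) + f

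| f | Coded negative | Blank, dropped | Blank, non-success |
|---|---|---|---|
| 5% | 0.23 × 0.95 = 21.9% | 23.0% | 26.9% |
| 10% | 0.23 × 0.90 = 20.7% | 23.0% | 30.7% |
| 20% | 0.23 × 0.80 = 18.4% | 23.0% | 38.4% |

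At f = 10%, 0.10 × 450 = 45 participants are tumour-free. The failures are 0.23 × 405 = 93.15, and 93.15 / 450 = 20.7%.

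**Why the first column is a maximum effect.** A tumour-free case that needs re-excision is a failure under the written definition. If some tumour-free cases fail this way, fewer than f are automatic successes, and the understatement is smaller than the fraction f.

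**Against sampling error.** At 20.7% with n = 450, the one-sided 95% half-width is 1.645 × √(0.207 × 0.793 / 450) = 3.1 points. The shift is 2.3 points at f = 10% and 4.6 points at f = 20%. For whole counts at f = 20%, using a 22.6% rate (the US re-excision figure): 81/360 = 22.5%, exact one-sided upper limit 26.4%; 81/450 = 18.0%, upper limit 21.2%. In that case the all-case upper limit lies below the margin-evaluable estimate.

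**The case against.** The strongest reply is that the direction is not established. A reader might infer that the plan has a rule scoring every tumour-free specimen as a success. It has none. The case report form is not among the documents and may hold an option the lists do not show. The schedules define negative as more than 2 mm, which cannot be measured without tumour, so a site could well leave the field blank. SAP section 6.4 then calls for analysis with and without imputation. This stands: counting as success follows from the literal definition, and the table shows the other outcomes. It does not remove the need for a rule, since the same data can give 18.4%, 23.0% or 38.4%.

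A reader might also infer that the endpoint will be set against the 23% and 22.6% re-excision rates. Only the primary endpoint has a planned historical comparison, and those rates cover re-excision alone, not the three-part composite.

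An all-case rate also has a basis in the documents. Protocol sections 3.1 and 9.2 describe a device for marking tissue to be removed for suspected as well as confirmed carcinoma. That is a reason to keep the all-case rate in the report.

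Finally, restricting the denominator to specimens with tumour would drop missed lesions, the localisation failures the endpoint ought to catch. This is correct, and the fix allows for it.

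The separate neoadjuvant analysis helps with one source of tumour-free specimens but leaves the overall rate unchanged. Pathology data already collected might allow a later reconstruction, but the denominator would then be chosen after the results were known.

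**Conclusion.** The point holds as a gap in the endpoint's definition and denominator. Read literally, the plan counts operated tumour-free cases as successes unless re-excision is required. That understates the failure rate among margin-evaluable cases by at most the fraction f: 1.1 to 4.6 percentage points for f of 5% to 20% at an assumed 23% failure rate. Both f and the 23% are assumptions. If sites leave the field blank, the estimate may be unbiased or show too high a failure rate, and sites that code differently would not be comparable.

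The consequence is limited. This is one of eight secondary endpoints, reported descriptively, with no pass/fail criterion and no planned historical comparison. It should be corrected before the database is locked, but it does not threaten the primary endpoint.

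**What to change.** 1. Add a margin response *not applicable: no invasive cancer or DCIS in specimen*, and state in SAP section 6.4 that it is not missing data and is not imputed.
2. In SAP section 9, make the main denominator of procedural success the operated participants whose specimen contains invasive cancer or DCIS, plus any participant whose target lesion was missed or who required re-excision. Count these added participants as failures.
3. Map the re-excision field to the endpoint in SAP section 7.1, so that such failures are captured.
4. Report alongside it the number of other tumour-free specimens, split into benign and no residual tumour after neoadjuvant therapy, and the all-case rate.

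The cost is one response option read from a pathology report already collected, a short addition to the SAP, and a stated way of identifying a missed lesion. The downside is a smaller denominator and a slightly less favourable success rate. No clinical procedure changes.
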